6 DOSING DELAYS/DOSE MODIFICATION

If a subject fails to meet criteria to start subsequent course (section 5.1.3) then treatment with investigational product should be delayed and the subject should be re-evaluated weekly. Any subject who fails to recover from a disease or treatment-related toxicity to baseline or \leq Grade 1 (except alopecia and Grade 2 fatigue) within 2 weeks of scheduled retreatment, or within 1 week of scheduled retreatment if toxicity is related to cytokine release, should discontinue the investigational product.

Subjects requiring more than 2 dose reductions, or dose reduction below dose level 0, must discontinue the investigational product.

Management of suspected adverse drug reactions may require temporary interruption and/or dose reduction of APX005M. If a subject experiences several toxicities, the recommended dose adjustment should be based on the highest grade toxicity. All dose reductions for APX005M, if required, will follow the dose levels defined in

Table 2.

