5.4.2 Off Treatment Criteria

At the discontinuation of treatment, the “Off Treatment Date” is to be recorded in the eCRF and is to be consistent with the reason given for going off treatment. The “Last Treatment Date” is defined as the last date that the patient received protocol based therapy. Date of “off treatment” must be the greatest of the date of last treatment, date of procedure, date of patient assessment, notification of patient/family decision, or decision made by the physician that resulted in the patient being taken off protocol treatment. The reason for discontinuation of treatment must be documented by the attending investigator in the medical record and recorded in the eCRF.

Patients will be considered Off Treatment for the following reasons:

- Development of unacceptable toxicity as outlined in section 5.2.1. See section 7 for specific reporting requirements.
- Progressive disease (PD) as described in section 11.3.
- Development of a medical or psychiatric illness that in the investigator's judgment renders the patient incapable of further therapy on this protocol or the treating physician determines continuation on this study is not in the patient's best interest.
- The patient, parent or legal guardian refuses further treatment on this protocol. In this case the investigator should clarify if the family also wishes to withdraw consent for continued participation for data collection purposes.
- Completion of all protocol defined treatment
- Pregnancy
- Non Compliance that in the opinion of the investigator does not allow for ongoing participation.

Patients who are off protocol therapy must be followed until an “Off Study Criterion” is met.

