6.2 Hematologic and Non-hematologic Adverse Events and Management

6.2.1 Dose Modifications for Hematologic Toxicity

Dose adjustments are based on nadir blood counts since the preceding administration of investigational product.

If a patient experiences dose-limiting hematological toxicity as outlined in Section 5.2.1.2, APX005M treatment will be reduced to the next lower dose level. If the toxicity resolves to meet on study parameters within 14 days of drug administration, provided there is no current active bleeding in the case of dose-limiting thrombocytopenia, the patient may resume therapy at one dose level lower. Patients who are dose-reduced for toxicity will not have their dose re-escalated. If toxicity does not resolve to meet on study parameters within 14 days of drug administration, the patient must be removed from protocol therapy. Two dose-reductions per patient are allowed. If any dose-limiting toxicity occurs in a patient already dose-reduced twice for toxicity, the patient must be removed from protocol therapy. APX005M dose adjustments for hematologic toxicity during treatment are described in Table 3.

Table 3: APX005M Dose Modifications for Hematologic Toxicity

APX005M related toxicity	APX005M dose modification
Grade 4 Neutrophil count decrease	Dose reduction
Grade 3 Neutrophil count decrease with fever	Dose reduction
Grade 4 Thrombocytopenia	Dose reduction
Grade 3 Thrombocytopenia on 2 separate days or requiring a platelet transfusion on 2 separate days within a 7 day period	Dose reduction

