6.2.2 Dose Modifications for Non-hematologic Toxicities

APX005M dose adjustments for non-hematologic toxicity during treatment are described in Table 4. All dose modifications should be made based on the worst preceding toxicity. For all toxicity \leq Grade 2, the current dose level should be maintained.

Table 4: APX005M Dose Modifications for Non-hematologic Toxicity

APX005M-related toxicity	Action taken with APX005M
Nausea/Vomiting Grade 4, or Grade 3 \geq 5 days	Dose reduction
Diarrhea Grade 4, or Grade 3 not responsive to optimal medical treatment for $>$ 5 days	Dose reduction
Cytokine release syndrome Grade 3 \leq 7 days	Dose reduction
Cytokine release syndrome Grade 3 $>$ 7 days	Discontinue APX005M
Cytokine release syndrome Grade 4	Discontinue APX005M

Other Grade \geq 3 toxicities (except alopecia) [§]	Adjust as medically indicated after discussion with study chair
--	---

[§] In the event of the “other” Grade 3 or 4 non-hematologic toxicities that, in the opinion of the Investigator, are unrelated to the investigational product, subject may continue on therapy with or without dose reduction only after documented discussion with the study chair.

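### The highest-grade rule in Section 6, read literally, gives a dose reduction where prolonged Grade 3 cytokine release syndrome requires discontinuation (4 toxicity pairs)

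*Combined protocol and SAP*

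**What the plan says.** Section 6 gives one rule for concurrent toxicities: "If a subject experiences several toxicities, the recommended dose adjustment should be based on the highest grade toxicity". The sentence before it reads "Management of suspected adverse drug reactions may require temporary interruption and/or dose reduction of APX005M", and the one after it ties reductions to the dose levels of Table 2.

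The actions themselves are in Sections 6.2.1 and 6.2.2. Every row of Table 3, such as "Grade 4 Neutrophil count decrease", leads to dose reduction. In Table 4, Grade 4 nausea/vomiting and Grade 4 diarrhea also lead to dose reduction, but the row "Cytokine release syndrome Grade 3 $>$ 7 days" leads to discontinuation, as does Grade 4 CRS. Section 6.2.2 adds a second rule: "All dose modifications should be made based on the worst preceding toxicity". It does not define *worst*. Neither section says that the strictest action governs.

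**The concern.** A highest-grade rule works only if the actions are ordered the same way as the grades. Within CRS they are: Grade 3 of up to 7 days is a reduction, and both Grade 3 beyond 7 days and Grade 4 are discontinuations. Across toxicity types they are not. A patient with prolonged Grade 3 CRS and, say, Grade 4 neutropenia has the neutropenia as the highest-grade event, and that row asks only for a reduction. A site applying the sentence as written could give another dose after a toxicity for which the same protocol requires a stop. The patients are children, and Section 5.1.1 records Stratum 2 as still open at this amendment, so the instruction can still affect care.

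**Working it through.** The plan states no figure on this point, so the check is an enumeration of the table rows.

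**Inputs.** Tables 3 and 4, with mixed-grade rows split into single-grade entries. The row for other Grade 3 or higher toxicities is set aside at first because its action is discretionary.

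| Grade | Entry | Action |
|---|---|---|
| 4 | neutropenia; thrombocytopenia; nausea/vomiting; diarrhea | reduce |
| 4 | CRS | discontinue |
| 3 | neutropenia with fever; qualifying thrombocytopenia; nausea/vomiting of 5 days or more; unresponsive diarrhea beyond 5 days; CRS up to 7 days | reduce |
| 3 | CRS beyond 7 days | discontinue |

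**Unequal grades.** There are 5 Grade 4 and 6 Grade 3 entries: 5 × 6 = 30 pairs. Same-toxicity pairs drop out (one each for neutropenia, thrombocytopenia, nausea/vomiting and diarrhea, two for CRS: 6), leaving 30 − 6 = 24.

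- Grade 4 CRS with a Grade 3 non-CRS entry: 4 pairs. The highest-grade rule gives discontinuation, which is right.
- Both entries lead to reduction: 16 pairs (4 × 3 with another non-CRS type, plus 4 × 1 with CRS up to 7 days). No conflict.
- A Grade 4 non-CRS entry with Grade 3 CRS beyond 7 days: 4 pairs. The rule gives reduction; the CRS row requires discontinuation.

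The total is 4 + 16 + 4 = 24, of which 4 are inverted. Adding the discretionary row gives one further pair, another Grade 4 toxicity with Grade 3 CRS beyond 7 days, where the rule points to a decision after chair discussion instead of a stop.

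**Equal grades, different toxicities, one reduction and one discontinuation.** Grade 4 CRS with each of 4 others, and Grade 3 CRS beyond 7 days with each of 4 others: 8 pairs. The highest-grade rule gives no answer.

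**What the inversion means in dose (Table 2).** From 0.6 mg/kg the next dose would be 0.45 (0.45/0.6 = 75%) or 0.3 (50%); from 0.3 it would be 0.1 (33%); from 0.1 it would be 0.03 (30%). Under the CRS row it would be none.

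**Where another fixed rule removes the inversion.**

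- Dose level 0, or two earlier reductions: "Subjects requiring more than 2 dose reductions, or dose reduction below dose level 0, must discontinue the investigational product".
- Slow recovery from CRS: Section 6 stops patients not recovered within 2 weeks of scheduled retreatment, "or within 1 week of scheduled retreatment if toxicity is related to cytokine release, should discontinue the investigational product". With a 21-day course that is 21 + 7 = 28 days after infusion. If CRS starts on the infusion day, an episode that lasts more than 7 days but has recovered by day 28 is not caught.
- The two hematologic pairs: Section 6.2.1 removes a patient whose dose-limiting hematologic toxicity has not returned to on-study parameters within 14 days of dosing. Section 3.1.9 sets these at ANC 1.0 × 10⁹/L and platelets 100 × 10⁹/L. These 2 of the 4 pairs therefore arise only if counts recover by day 14.

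**With a most-restrictive-action rule,** 0 of the 4 inversions remain and all 8 ties resolve to discontinuation.

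**The case against.** The best defense is the position of the sentence. It stands between one about interruption and reduction and one about reductions only, so it can be read as choosing among those, with discontinuation fixed separately by the CRS row. The Section 6.2.2 wording about the worst toxicity can also accommodate a row that requires stopping. A careful investigator would probably stop. This reading is plausible, but the text does not secure it: Section 6.2.2 introduces Table 4, discontinuations included, as describing dose adjustments, which is the term the Section 6 sentence uses.

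Other provisions soften the consequence without settling which action wins:

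- Section 5.1.3 holds the next course until drug-related toxicity is back to baseline or Grade 1 at most, with two named exceptions. That delays a dose; it does not forbid it.
- Section 5.1.2 starts the next infusion at half rate after such a reaction, and stops permanently if symptoms recur at that rate despite treatment.
- Section 6.1 requires notice of every dose modification to the chair or co-chair, but gives no decision rule.
- Section 5.4.2 lists "Development of unacceptable toxicity as outlined in section 5.2.1" as a reason to go off treatment. That section covers Grade 3 or higher CRS, but also events for which Tables 3 and 4 only reduce the dose, so it cannot rank the actions.

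It is also fair to say that the combination is likely rare. Section 2.2 places most adverse events within 48 hours of dosing, and Section 2.2.2 reports neutropenia no worse than Grade 3 in Stratum 1. Both observations stand and keep the severity low.

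**Conclusion.** The point holds as a low-severity conflict in a safety instruction. On the literal reading, 4 of 24 cross-toxicity pairs give a milder action than the CRS row requires, and 8 equal-grade pairs are undecided. This rests on counting only rows with a fixed action and on taking *dose adjustment* to include discontinuation, as Section 6.2.2 does. Two of the 4 pairs are narrowed further by the 14-day hematologic rule.

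Three stronger readings are not supported.

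- A reader might infer that the tables generally fail to escalate with grade. Within CRS they do escalate; the inversion appears only across toxicity types.
- A reader might try to bound the frequency from Stratum 1, where no DLT is reported as CRS. Such a bound would describe any Grade 3 or higher CRS, not CRS beyond 7 days together with a Grade 4 event. The Table 5 footnote also directs reactions during or shortly after infusion to be coded as infusion-related reactions, and both Stratum 1 DLTs were Grade 3 infusion-related reactions. The count of zero is therefore uninformative. Nor is a pair documented in adults: Section 2.2 mentions Grade 3 CRS and Grade 4 thrombocytopenia at 1 mg/kg, but as events among two subjects.
- A reader might suspect an effect on dose finding. Section 5.2.1 counts a related event in the first two courses as a DLT whether it leads to reduction or to permanent cessation, so DLT counts and escalation do not change.

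**What to change.** Replace the Section 6 sentence with wording such as:

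*When more than one toxicity is present, each is assessed against Sections 6.2.1 and 6.2.2, and the most restrictive action required by any of them applies (discontinuation over dose reduction). Any study chair discussion required for an Other Grade ≥ 3 toxicity still takes place and may lead to a stricter action, but not a milder one.*

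Use the same rule in Section 6.2.2 in place of the reference to the worst toxicity. The second sentence is needed because a plain ranking with chair discussion below reduction would let an automatic reduction, for example for Grade 3 vomiting, displace the discussion required for a serious toxicity without its own row.

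The cost is one replaced sentence and matching wording at the next amendment, with no added patients, data or analyses. The downside is that a few patients may be reduced or discontinued who would otherwise stay on a higher dose.

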6.1 Notification of the Study Chair

The study chair or co-chair must be notified of any dosage modifications.

6.2 Hematologic and Non-hematologic Adverse Events and Management

6.2.1 Dose Modifications for Hematologic Toxicity

Dose adjustments are based on nadir blood counts since the preceding administration of investigational product.

If a patient experiences dose-limiting hematological toxicity as outlined in Section 5.2.1.2, APX005M treatment will be reduced to the next lower dose level. If the toxicity resolves to meet on study parameters within 14 days of drug administration, provided there is no current active bleeding in the case of dose-limiting thrombocytopenia, the patient may resume therapy at one dose level lower. Patients who are dose-reduced for toxicity will not have their dose re-escalated. If toxicity does not resolve to meet on study parameters within 14 days of drug administration, the patient must be removed from protocol therapy. Two dose-reductions per patient are allowed. If any dose-limiting toxicity occurs in a patient already dose-reduced twice for toxicity, the patient must be removed from protocol therapy. APX005M dose adjustments for hematologic toxicity during treatment are described in Table 3.

Table 3: APX005M Dose Modifications for Hematologic Toxicity

APX005M related toxicity	APX005M dose modification
Grade 4 Neutrophil count decrease	Dose reduction
Grade 3 Neutrophil count decrease with fever	Dose reduction
Grade 4 Thrombocytopenia	Dose reduction
Grade 3 Thrombocytopenia on 2 separate days or requiring a platelet transfusion on 2 separate days within a 7 day period	Dose reduction

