3.1.9 Organ Function

Patients must have adequate organ and bone marrow function as defined below:

- Absolute Neutrophil Count (ANC) ≥ 1.0 x 10⁹ cells/ L
- Platelets ≥ 100 x 10⁹ cells/L (unsupported, defined as no platelet transfusion within 7 days)
- Hemoglobin ≥ 8 g/dL (may receive transfusions)
- Total bilirubin ≤ 1.5 times institutional upper limit of normal (ULN)
- AST(SGOT)/ALT(SGPT) ≤ 3 x institutional upper limit of normal (ULN)
- Albumin ≥ 3 g/dl
- Serum creatinine based on age/gender as noted in Table 1. Patients that do not meet the criteria in Table 1 but have a 24 hour Creatinine Clearance or GFR (radioisotope or iothalamate) ≥ 70 mL/min/1.73 m² are eligible.

Table 1

Serum Creatinine for age/gender		
Age	Maximum Serum Creatinine (mg/dL)	
	Male	Female
1 to < 2 years	0.6	0.6
2 to < 6 years	0.8	0.8
6 to < 10 years	1	1
10 to < 13 years	1.2	1.2
13 to < 16 years	1.5	1.4
≥ 16 years	1.7	1.4

The threshold creatinine values in this Table were derived from the Schwartz formula for estimating GFR (Schwartz et al. J. Peds, 106:522, 1985) utilizing child length and stature data published by the CDC.

- Cardiac Function:
 - Left Ventricular Ejection Fraction (LVEF) > 50%
 - ECG QTc ≤ 450 msec
- Pulmonary Function:
 - Oxygen saturation as measured by pulse oximetry is > 93% on room air and no evidence of dyspnea at rest

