5.1.3 Criteria to Start Subsequent Courses

A course may be repeated every 3 weeks if the patient has at least stable disease, all drug-related toxicities return to baseline or \leq Grade 1 (excluding alopecia and Grade 2 fatigue) and has again met laboratory parameters as defined in Section 3.1.9. If a patient does not meet these parameters at the end of the treatment course then APX005M should be held until parameters meet the eligibility criteria.

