5.2.1 Dose-Limiting Toxicities (DLT's)

- Any APX005M-related adverse event during the first 2 courses of therapy (6 weeks, 42 days) that leads to a dose reduction or results in the permanent cessation of therapy will be considered dose limiting. All dose modifications in all courses are to follow the guidelines provided in Section 6.2.
- Any APX005M-related adverse event during the first 2 courses of therapy that results in a delay of treatment > 2 weeks.

5.2.1.1 Non-hematologic dose limiting toxicity is defined as:

- Any grade 4 non-hematologic toxicity
- Any grade 3 non-hematologic toxicity with the exception of:
 - Grade 3 nausea and vomiting < 5 days
 - Grade 3 diarrhea responding to optimal medical treatment within 5 days
 - Grade 3 elevation of transaminases that returns to levels meeting eligibility criteria within 7 days of study drug interruption and does not recur upon restarting drug.
 - Grade 3 fever or infection of fewer than 5 days in duration

- Grade 3 hypophosphatemia, hypokalemia, hypocalcemia or hypomagnesemia that are asymptomatic and responsive to oral supplementation
- Grade ≥ 3 cytokine release syndrome
- Toxicity related to treatment with APX005M which delays scheduled re-treatment for > 2 weeks, or >1 week for cytokine release related complications.

5.2.1.2 Hematologic dose limiting toxicity is defined as:

- Any grade 4 hematologic toxicity with the exception of lymphopenia
- Grade 3 neutropenia with fever
- Grade 3 thrombocytopenia on 2 separate days or requiring a platelet transfusion on 2 separate days within a 7 day period.

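### Section 6.2.1, read literally, takes a patient off treatment if a haematologic DLT has not resolved by day 15, a week before the next dose is due, and so defeats its own dose-reduction rule for later-onset events

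*Combined protocol and SAP*

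**What the plan says.** All places are in the combined protocol and SAP.

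- **6.2.1 and Table 3.** "Dose adjustments are based on nadir blood counts since the preceding administration of investigational product". A patient with a haematologic DLT as defined in 5.2.1.2 goes down one dose level. All four rows of Table 3 give dose reduction as the action, with no condition on the day of onset. The patient may resume at the lower level if counts are back to on-study parameters inside the 14 days (and, for thrombocytopenia, there is no active bleeding). Otherwise: "If toxicity does not resolve to meet on study parameters within 14 days of drug administration, the patient must be removed from protocol therapy".
- **Section 6.** A patient who has not returned to baseline or grade 1 "within 2 weeks of scheduled retreatment, or within 1 week of scheduled retreatment if toxicity is related to cytokine release, should discontinue the investigational product". Until then dosing is delayed and the patient is re-evaluated weekly.
- **5.1.3.** "If a patient does not meet these parameters at the end of the treatment course then APX005M should be held" until the eligibility limits are met again.
- **5.2.1.** Its delay criterion also counts from the due date: "Toxicity related to treatment with APX005M which delays scheduled re-treatment for > 2 weeks". The section also makes 6.2 the text that sites apply: "All dose modifications in all courses are to follow the guidelines provided in Section 6.2".
- **5.4.2.** Unacceptable toxicity, defined by reference to 5.2.1, is a reason for going off treatment. Section 5.2.1 contains the haematologic DLTs.
- **Section 10.** Blood counts are weekly in courses 1 and 2, then once before each course. Footnote B allows more where toxicity needs monitoring.

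**The concern.** Two clocks govern the same patient. In Sections 6, 5.1.3 and 5.2.1 recovery is judged at or after the date the next dose falls due. In 6.2.1, taken at its word, the clock starts at the dose already given and runs out before the next one is due.

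The difference is more than one of strictness. Section 6.2.1 tells the site to act on the lowest count over the whole interval since the last dose and to reduce the dose. It then sets a recovery deadline that falls two-thirds of the way through that interval. For an event that begins in the last third, the two instructions cannot both be followed.

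At stake is whether a child whose counts recover in time for the next dose continues at a lower dose or is taken off treatment, and whether sites apply the same limit.

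**Working it through.** **Scale check.** Dose on day 1 of a 21-day course (5.1.1). Two courses = 2 × 21 = 42 days, as in 5.2.2. Thirty-six courses = 36 × 21 = 756 days = 2.07 years, agreeing with the roughly 2 years in 5.1.1.

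**Limits, counted from the dose on day 1**

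| Event | Arithmetic | Day |
|---|---|---|
| 6.2.1 limit, literal | 1 + 14 | 15 |
| Next dose due | 1 + 21 | 22 |
| Section 6 limit | 22 + 14 | 36 |
| Section 6 limit, cytokine release | 22 + 7 | 29 |

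Gap between 6.2.1 and Section 6: 36 − 15 = 21 days. It has two parts: days 16–22 (7 days), where a recovered patient is removed with no dose missed, and days 23–36 (14 days), where Section 6 would allow a delay.

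**Can the reduction be reached?** A DLT first present after day 15 cannot have resolved by day 15, so the literal result is removal. The scheduled counts leave little room even for earlier events:

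- Courses 1–2: post-dose counts on days 8, 15 and 22. Only day 8 leaves time (15 − 8 = 7 days), so 1 of 3.
- Courses 3–36: one count before the next course, nominally day 22. If the 7-day laboratory window of 3.4 is assumed to carry over, the earliest is 22 − 7 = day 15, leaving 0 days.

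Extra counts under footnote B help only if the event is both found and resolved by day 15.

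**Transfused patients.** One DLT route is "Grade 3 thrombocytopenia on 2 separate days or requiring a platelet transfusion on 2 separate days within a 7 day period", and on-study platelets (3.1.9) must be "unsupported, defined as no platelet transfusion within 7 days". If day 15 counts as within 14 days of day 1, then day 8 counts as within 7 days of day 15. The last compatible transfusion is therefore 15 − 8 = day 7 under 6.2.1 and 36 − 8 = day 28 under Section 6.

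**PK samples per patient (9.1.2.1).** 5 + 5 + 2 + 2 = 14 over courses 1–4. Removal after course 1 loses 9 (64%), after course 2 loses 4 (29%), after course 3 loses 2 (14%).

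**Frequency (2.2.2).** Both Stratum 1 DLTs were grade 3 infusion-related reactions, so there were 0 haematologic DLTs in 3 + 3 + 12 = 18 patients, assuming all six at dose levels 1 and 2 were evaluable. The exact two-sided 95% upper limit is 1 − 0.025^(1/18) = 18.5%. Applied to the 12 patients planned for Stratum 2, 12 × 0.185 = 2.2. So 0 to about 2 patients is the range within the first two courses. It is a bound, not an estimate.

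**The case against.** **Intent.** The 14 days in 6.2.1 equal the two weeks in Section 6, and the companion sentence is about when treatment may resume. The authors may well have meant 14 days from the dose that is due. That is plausible and probably right, but the text does not say it, and the opening sentence of 6.2.1 uses administration for the dose already given. If this is the intent, the fix simply states it.

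**Specific overrides general.** Section 6 sets an outer limit and 6.2 may be tighter. Table 4 does this for cytokine release syndrome: grade 3 lasting more than 7 days means discontinuation, while Section 6 alone would allow until day 29. This stands against any claim that a limit shorter than Section 6 is wrong in itself, and caution is defensible in a first paediatric study. It does not remove the conflict inside 6.2.1 for late-onset events.

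**Study chair.** Section 6.1 requires the chair or co-chair to be told of any dose modification. That may catch a case, but it does not change a mandatory removal.

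**5.4.2.** On an equally literal reading, any 5.2.1 DLT is already an off-treatment criterion, so correcting 6.2.1 alone would not secure the Table 3 reduction. This stands, and the fix covers it.

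**Rarity.** This also stands. Section 2.2.2 gives neutropenia a maximum of grade 3, so the grade 4 neutrophil row of Table 3 is not among the events reported there. A reader might infer from the maximum of grade 4 for leukopenia that a haematologic DLT did occur. The documents do not support that: the grades are not tied to attribution or to the first two courses, and the only DLTs reported are infusion reactions.

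**Conclusion.** The point holds as a drafting conflict of low severity. As written, 6.2.1 requires removal on day 15 for an unresolved haematologic DLT, 7 days before the next dose and 21 days before the Section 6 limit. It makes the ordered dose reduction unreachable for any such event first present after day 15. The one exception is trivial: an event that arose and resolved earlier but was reported late.

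This rests on the literal reading of administration as the preceding dose, and on reading on-study parameters as the limits in 3.1.9.

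Three stronger readings are tempting and should be resisted:

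- *That the sponsor chose a day-15 limit.* The wording yields it, but nothing in the documents shows it was intended.
- *That dose finding or efficacy data are compromised.* The event is a DLT under 5.2.1.2 whichever limit applies, and patients removed for toxicity stay evaluable for the MTD (11.1.1). DLT counts and escalation are therefore unchanged. Stratum 2 patients are followed off treatment (5.4.3, 5.4.4), so PFS and OS collection is unaffected.
- *That the trial stands to lose 64% of its PK data.* That figure is for one patient removed after course 1.

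What remains is the effect on individual discontinuations, exposure and later PK samples, at a frequency that the documents do not establish.

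**What to change.** 1. In both sentences of 6.2.1 that set the 14-day limit, replace the reference point so that the limit is 2 weeks from scheduled retreatment, as in Section 6.
2. In 5.4.2, refer unacceptable toxicity to the discontinuation rules in Section 6 instead of 5.2.1, so that a DLT eligible for dose reduction is not also an off-treatment criterion.

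The cost is two phrases and one cross-reference in the next amendment. Nobody is dosed before recovery, because 5.1.3 still has to be met. That section requires both the laboratory limits and grade 1 or baseline, so the different recovery thresholds in 6.2.1 and Section 6 do not open a gap. The downside is that a slow recoverer may stay on protocol, undosed and re-evaluated weekly, for up to 21 more days (day 15 to day 36). The documents give no recovery-time data to favour either limit.

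If the sponsor does want a shorter limit, it should start from a point that lets Table 3 operate, and the text should say what happens to a DLT first seen after day 15.
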